As mentioned above, the concept of va-ECMO in resuscitated patients is to disburden vital organs in a critical phase and thus to facilitate their recovery under supportive intensive care and/or to get time to initiate further procedures in order to eliminate the original cause for cardiopulmonary arrest.

In this study, we aim to show, whether patients after CPR with subsequent va-ECMO profit from an additional modulation of the inflammatory reaction via hemoadsorption (Cytosorb®) in terms of levels of inflammatory cytokines and ultimaltely in organ function and survival.

4. Prior Knowledge

Patients with cardiopulmonary arrest and subsequent CPR are regularly harmed by a subsequent systemic inflammatory reaction with many parallels to those suffering from sepsis. In both groups, there is a significant increase in the levels of pro-inflammatory cytokines as interleukin 6 (IL-6). According to present data, there seems to be a positive correlation between the individual level of this increase and terminal mortality of the patients (1).

With hemoadsorption (Cytosorb®, MedaSorb Technologies, Princeton, N.J., USA), a device for effective elimination of cytokines like tumor necrosis factor α (TNF- α), interleukine 6 (IL-6) and 8 (IL-8) from the patient's bloodstream is available. This device is CE-certified for a use in extracorporal circulation and has been in clinical use worldwide for successful adsorbtion of cytokines, yet as to our knowledge never for routine elimination of circulating cytokines in a post-resuscitation setting so far.

Previous studies were able to establish the capability of the Cytosorb adsorber to eliminate IL-6, interleukine 10 and TNF- α from the serum and reduce the mortality under severe sepsis in an animal model (2).

As for the clinical application in humans, there are several case reports attributing a positive outcome for severely affected patients to the use of hemoadsorption. A significant reduction of cytokines by the device has been shown in patients under sepsis (4), systemic inflammation caused by sepsis (5) and systemic inflammation without sepsis (6) (own publication, *submitted*).

As to our knowledge, there is currently no data available for the application of this device in severe systemic inflammation after cardiac arrest, CPR or va-ECMO subsequent to the named conditions.

5. Study Conception and Project Outline

5.1 primary and secondary endpoints

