In this study, we aim to show that hemoadsorption (Cytosorb®) is a viable option to reduce serum levels of proinflammatory cytokines in patients under va-ECMO after CPR. Specifically, our hypothesis constitutes significantly lower levels of IL-6 and TNF- α in patients undergoing hemoadsorption for 48 hours compared to a control group receiving standard medical care at va-ECMO during a 72 hours-timeframe.

Primary outcome parameters

Laboratory parameters expressing an inflammatory response constitute the primary outcome of our study. Thus,

IL-6, TNF-a, S1P, PCT, CRP, leucozytes

are to be measured at time points 0,6,12,24,48 and 72 hours after administration to va-ECMO.

Secondary outcome parameters

Those are supposed to reflect secondary and tertiary effects of the hemoadsorption on organ function and overall survival of the patients:

- 1. Laboratory and clinical parameters of inflammation and organ damage/dysfunction (cardiovasculary, pulmonary, hepatic, renal, neuronal):
 - NSE, (free) hemoglobine, haptoglobine, BNP, Troponine, Creatinekinase, Myoglobin, GOT, GPT, Creatinine
 - cardiovasculary: (MAP, CVP, HR,. echocardiographic parameters)
 - pulmonary: oxygenation/decarboxylation, acid-base-balance by blood gas analysis

- 2. Parameters of treatment:
 - Cardiovasculary: Dependence on inotropics, and vasopressors, volume substitution or elimination,
 - pulmonary: relevant parameters of ventilation
 - additional organ replacement therapy (dialysis, hepatic replacement)
- 3. Parameters of terminal outcome
 - mortality within the first 30 days after inclusion into the study
 - length of stay in intensive care/in hospital

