5.3 Sample size

We expect a difference of 20-30% in serum concentration of IL-6 at 24 hours after inclusion (about 60µg/L difference at total levels of 200-300µg/L, standard deviation 90µg/L). With 18 patients per group, the study could determine a significant difference between the groups with a power of 90% and an error propability of 5% by ANOVA. To attribute for post-hoc exclusion or drop-out of participants with an estimated rate of 10%, we suggest a sample size of 20 patients per group, adding to a total of 40 participants in the study

This calculation is based on the publication of Adrie C. Et al. (1) and on a previous study performed in our department (publication pending).

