5.6 Randomization

Randomization is performed at the time of establishment of va-ECMO. Drawing without returning of prepared sealed envelopes will ensure an identical size of 20 participants each for control and intervention groups .

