5.7. Statistical analysis

Statistical analysis is conducted using the software package SPSS. To characterize the patients, we are going to conduct descriptive analytics in dependence on the statistical distribution of variables.

Continuous variables like hemodynamic and laboratory parameters are analyzed using a multifactorial ANOVA or a mixed lineary model.

Nominal or categorized variables are going to be analyzed in four-to-multi-square-tables with chi-square-tests or Fisher's exact test.

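### Length of stay falls under the general ANOVA or mixed-model rule with no provision for death, so a difference in deaths between the arms can appear as a difference in stay

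*Protocol*

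**What the plan says.** Section 5.1 (secondary outcome parameters, item 3, terminal outcome) has two separate entries: "mortality within the first 30 days after inclusion into the study" and "length of stay in intensive care/in hospital". The second has no time horizon, no definition and no rule for a stay that ends in death.

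Section 5.7, Statistical analysis, gives two classes of comparison. The first reads "Continuous variables like hemodynamic and laboratory parameters are analyzed using a multifactorial ANOVA or a mixed lineary model". The second reads "Nominal or categorized variables are going to be analyzed in four-to-multi-square-tables with chi-square-tests or Fisher's exact test". The section also promises descriptive statistics, but to characterise the patients. Length of stay is not mentioned there. No time-to-event method, competing-event method, days-alive measure or rank rule for deaths appears anywhere in the protocol.

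Two other statements matter here. Section 4 says of the cytokine rise that "there seems to be a positive correlation between the individual level of this increase and terminal mortality of the patients". Section 5.6 says the envelopes will "ensure an identical size of 20 participants each for control and intervention groups".

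**The concern.** All participants have had a cardiac arrest and are on va-ECMO, so deaths during the stay must be expected. Days in intensive care or hospital then mix two opposite courses: a patient who recovers quickly and a patient who dies early both have a low value. A comparison of mean stay cannot tell them apart.

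Section 5.1 says the secondary outcomes are meant to show later effects of the adsorber on organ function and survival, and section 4 ties cytokine level to mortality. A difference in deaths between the arms is therefore an effect the trial itself considers possible, and it is also what distorts this outcome. The distortion can run either way. Excess early deaths can shorten the mean stay, and a real survival benefit can lengthen it.

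**Working it through.** The protocol states no figure for length of stay or mortality, so there is none to reproduce. The check has three parts.

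**1. Which rule applies.** Length of stay is a number of days. Of the two classes in section 5.7, Statistical analysis, only the one for continuous variables fits. This is an inference from the general rule, because the outcome is not named.

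**2. Size of the distortion.** All inputs here are assumptions: m is the mortality in an arm, S the mean stay of survivors and D the mean stay of non-survivors. S and D are taken as equal in both arms, so treatment has no effect on stay apart from its effect on death.

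Mean stay = (1 − m) × S + m × D

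With S = 25 and D = 4:
- m = 50%: 0.50 × 25 + 0.50 × 4 = 14.5 days
- m = 65%: 0.35 × 25 + 0.65 × 4 = 11.35 days
- m = 70%: 0.30 × 25 + 0.70 × 4 = 10.3 days

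The arm with more deaths has a mean stay shorter by 3.15 days (50% v 65%) or 4.2 days (50% v 70%).

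In general the difference is (m₂ − m₁) × (S − D). For a 20-point excess in mortality, with S from 15 to 25 and D from 2 to 7:
- smallest: 0.20 × (15 − 7) = 1.6 days
- largest: 0.20 × (25 − 2) = 4.6 days

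Timing alone can do the same. With 60% mortality in both arms and equal S, mean non-survivor stays of 2 v 7 days give 0.60 × (7 − 2) = 3.0 days.

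**3. How often this would show at 20 per arm.** The simulation used 20,000 trials, a two-group t-test (the same as a two-group ANOVA), survivor stays with mean 20 days (gamma, shape 4) and non-survivor stays with mean 4 days (exponential).

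| Mortality, arm A v arm B | Arm B has shorter mean stay | Arm B nominally significantly shorter |
|---|---|---|
| 60% v 60% | 50% | 2.4% |
| 50% v 70% | 84% | 16% |
| 60% v 80% | 86% | 18% |
| 50% v 80% | 94% | 34% |

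With equal mortality and equal timing, neither arm is favoured and the two-sided error is 4.8%. The distortion therefore comes from the difference in deaths and not from the test.

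**The case against.** The case on the other side has several parts, and much of it limits the point.

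- *The plan does not say that length of stay goes into the ANOVA.* Correct. A reader might infer a firm commitment to that analysis. The protocol supports only that the outcome falls there by default, as the only class that fits.
- *Nothing says a shorter stay counts as benefit.* Also correct. It is tempting to conclude that the plan scores early death as a good result, but no direction or hypothesis is set for this outcome. The stated hypothesis concerns IL-6 and TNF-α. What stands is that the mean can move in a misleading direction, whatever meaning a reader gives it.
- *Harm would not be hidden.* One might infer that excess deaths would pass unseen as a shorter stay. Mortality to day 30 is listed directly above and would be reported alongside, and the overview table names only mortality under terminal outcome. No sample size or decision in the protocol depends on length of stay. This lowers the weight but does not make the comparison of stay interpretable.
- *A statistical analysis plan may settle it.* It may, and handling of deaths is often put there. But the protocol lists the outcome and states a general rule that covers it, and nothing points to an exception.
- *The size is assumed.* It is. The effect needs a difference in deaths or in their timing, and at 50% v 70% a nominally significant result is uncommon (16%).

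**Conclusion.** The point holds as a modest one. Applied as written, the general rule for continuous variables gives a comparison of length of stay that confuses early death with early recovery, in a population where deaths must be expected. Under assumed mean stays of 15 to 25 days for survivors and 2 to 7 for non-survivors, a 20-point difference in mortality shifts the mean by 1.6 to 4.6 days towards a shorter stay in the arm with more deaths. With 25 and 4 days and mortality of 50% v 70%, the means are 14.5 v 10.3 days.

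The conclusion rests on two things: reading length of stay into the continuous class, and some difference in deaths or their timing between the arms. The direction holds whenever non-survivors stay for less time than survivors. The size depends wholly on the assumed figures. The primary cytokine outcomes are not affected.

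**What to change.** State in the protocol, or in the analysis plan before data are compared by arm, one of these for all randomised patients:

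- Days alive and out of intensive care, and separately out of hospital, within 30 days of inclusion, compared by a rank test. Death by day 30 takes the worst rank, below survivors still in care at day 30. Scoring both as zero would tie the dead with those survivors, and with survivor stays near 25 days there could be many.
- Time to discharge alive, with death as a competing event.

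Report raw length of stay, split by survival status, as description only. A test among survivors alone would compare groups no longer formed by randomisation.

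The days-alive measure removes the reversal in the example. At 50% v 70% mortality, 0.50 × 20 = 10 and 0.70 × 20 = 14 patients take the worst rank. With a fixed survivor stay of 25 days, survivors have 30 − 25 = 5 days each, so counting the dead as zero the means are 0.50 × 5 = 2.5 v 0.30 × 5 = 1.5 days. The arm with more deaths now does worse.

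The change is mainly one of wording, but not free. Stays beyond 30 days are capped under the days-alive measure. Discharge dates, and any readmission within 30 days, must be recorded. The protocol asks for length of stay and 30-day mortality but does not explicitly ask for these.

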5.2 Principal study desing

The study is single-centered, prospective, controlled and randomized.

5.3 Sample size

We expect a difference of 20-30% in serum concentration of IL-6 at 24 hours after inclusion (about 60µg/L difference at total levels of 200-300µg/L, standard deviation 90µg/L). With 18 patients per group, the study could determine a significant difference between the groups with a power of 90% and an error propability of 5% by ANOVA. To attribute for post-hoc exclusion or drop-out of participants with an estimated rate of 10%, we suggest a sample size of 20 patients per group, adding to a total of 40 participants in the study

This calculation is based on the publication of Adrie C. Et al. (1) and on a previous study performed in our department (publication pending).

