	of 200-300µg/L, standard deviation 90µg/L). With 18 patients per
	group, the study could determine a significant difference between
	the groups with a power of 90% and an error of propability of 5%
	by ANOVA.
	To attribute for post-hoc exclusion or drop-out of participants, we
	suggest a sample size of 20 patients per group, adding to a total of
	40 participants in the study.
randomization	Randomization is performed as drawing without returning to
	ensure an identical size for control and intervention groups

Hamburg, 29.12.2017

6. Literature

6. Bernardi MH, Rinoesl H, Dragosits K, Ristl R, Hoffelner F, Opfermann P, et al. Effect of hemoadsorption during cardiopulmonary bypass surgery - a blinded, randomized, controlled pilot study using a novel adsorbent. Critical care. S016;20:96.

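### The 90% power in section 5.3 and the Overview does not follow from the stated inputs: for the 24-hour IL-6 comparison they give about 49%

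*Protocol*

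**What the plan says.** Section 5.3 ties the sample size to one variable at one time point: "We expect a difference of 20-30% in serum concentration of IL-6 at 24 hours after inclusion". It puts this in absolute terms as "about 60µg/L difference at total levels of 200-300µg/L", with "standard deviation 90µg/L". From these inputs, a 5% error probability and an unspecified ANOVA, it concludes: "With 18 patients per group, the study could determine a significant difference between the groups with a power of 90" percent. A 10% allowance for drop-out then raises 18 to 20 per group, 40 in all. Section 5.3 bases the calculation on one cited publication and one departmental study not yet published, but takes no further parameter from either.

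The sample-size entry of the Overview carries the same inputs and the same claim ("the groups with a power of 90% and an error of propability of 5" percent).

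Two other places bear on the reading. Section 5.1 states the hypothesis for IL-6 and TNF-α "compared to a control group receiving standard medical care at va-ECMO during a 72 hours-timeframe", with measurements at 0, 6, 12, 24, 48 and 72 hours. The statistical analysis section says: "Continuous variables like hemodynamic and laboratory parameters are analyzed using a multifactorial ANOVA or a mixed lineary model".

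**The concern.** A standardised difference of about two thirds with 18 patients per group is well short of 90% power in an ordinary two-group comparison. Section 5.3 supplies everything needed to compute power for the 24-hour comparison, so the figure can be checked directly, and it fails.

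This calculation is the only justification for 40 patients, in an emergency setting where consent is sought after inclusion. A reader who trusts 90% would take a non-significant 24-hour result as fair evidence against a 60 µg/L effect. At 49% power such a result says little.

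**Working it through.** **Inputs, all from section 5.3:** difference δ = 60 µg/L, standard deviation σ = 90 µg/L, n = 18 evaluable per group (20 before drop-out), α = 0.05, ANOVA. Sidedness is not stated, but the F test for two groups equals the two-sided t-test. Allocation is 1:1 (section 5.6).

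**1. The stated figure, tested on its own inputs.** The noncentrality is δ / (σ√(2/n)), with 2n − 2 degrees of freedom.
- n = 18: 60 / (90 × √(2/18)) = 60/30 = 2.00. The critical t on 34 df is 2.032. Power = **49.3%**.
- n = 20: noncentrality 2.108, critical t on 38 df is 2.024. Power = **53.8%**.

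The stated 90% is not reproduced; the gap is about 40 percentage points. The drop-out step does reproduce: 18/(1 − 0.10) = 20.

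**2. More generous or stricter readings of the same inputs (n = 18 unless stated).**

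| Reading | Power |
|---|---|
| Normal approximation, two-sided | 51.6% |
| One-sided 5% | 62.4% (66.5% at n = 20) |
| Largest difference, 30% of 300 = 90 µg/L, two-sided | 83.0% |
| Smallest difference, 20% of 200 = 40 µg/L, two-sided | 25.4% |

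Only the 90 µg/L difference combined with a one-sided test reaches 90% (90.2%). Section 5.3 states neither, and an ANOVA F test is not one-sided.

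**3. What 90% would take for the 24-hour comparison.**
- Detectable difference at σ = 90: 100.1 µg/L with n = 18; 94.7 µg/L with n = 20.
- Standard deviation at δ = 60 and n = 18: about 54 µg/L.
- Sample size at 60/90: 49 evaluable per group, or 49/0.9 = 54.4, so 55 per group after 10% drop-out.

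**4. Could another analysis yield 90%?** Every correlation r and average effect below is an assumption, because the protocol gives none. σ² is multiplied by a variance factor; n = 18 per group.
- *Baseline-adjusted mean of the five values from 6 to 72 hours, equal correlation between all visits, average difference 60 µg/L.* Factor (1 + 4r)/5 − r², 33 df. It is largest at r = 0.4: 2.6/5 − 0.16 = 0.36. Power: 92.9% at r = 0.2, 89.9% at r = 0.4, 90.7% at r = 0.5, 96.2% at r = 0.7. A simulation of 20,000 trials gave 92.1%, 89.1%, 90.1% and 96.0%. Under equal correlation, power is therefore about 90% or more whatever r is.
- *Same model, correlation decaying by visit (AR(1)).* Lag-one correlation 0.5, 0.6, 0.7, 0.8: 86.0%, 82.7%, 81.2%, 83.7%.
- *Same model, equal correlation r = 0.4, smaller average effect.* 45 µg/L: 68.0%; 40 µg/L: 57.8%.
- *Unadjusted mean of the five values.* Factor (1 + 4r)/5: 89.9% at r = 0.2, 70.8% at r = 0.5. It needs r of about 0.20 or less.
- *24-hour value adjusted for baseline.* Factor 1 − r²: 61% at r = 0.5. It needs r of about 0.80.

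Across these scenarios power runs from about 58% to 96%, and section 5.3 states none of the quantities that decide where in that range the trial lies.

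**The case against.** The best defence is that the 24-hour value was only the source of the effect size, and that the ANOVA meant is the multifactorial or mixed model of the statistical analysis section, applied to six time points for a hypothesis that spans 72 hours. The correlation could come from the publication or the unpublished study on which section 5.3 relies.

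Part of this stands. A baseline-adjusted repeated-measures analysis can reach about 90% with 18 per group, so it would be wrong to say that the trial as a whole has 49% power. The justification also cannot be called uncheckable in general, only uncheckable from the protocol.

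It does not rescue the printed figure. Section 5.3 names one time point and gives no repeated-measures model, no effect over time and no correlation, and the statistical analysis section leaves the choice of model open. The defence shows that 90% is possible under added assumptions, not that it follows from those stated. A constant 60 µg/L from 6 to 72 hours is itself a strong assumption, since hemoadsorption is planned for 48 hours and the average runs to 72. A later statistical analysis plan may fix the model, but it does not correct a power statement that disagrees with the inputs printed beside it.

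**Conclusion.** The concern holds. For the comparison that section 5.3 describes, power is about 49% with 18 evaluable patients per group and 54% with 20, against a stated 90%. This rests only on the section's own difference, standard deviation, group size and error level, read as a two-sided two-group test. A one-sided test does not close the gap, nor does the largest difference the text allows, taken two-sided. The conclusion is limited to the 24-hour comparison. Power under a repeated-measures model remains open until the model, the average effect and the correlation are stated. Because the figure is the sole basis for the sample size and appears twice, it must be corrected.

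**What to change.** Change section 5.3 and the sample-size entry of the Overview together, in one of two ways.

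1. **If the 24-hour comparison is the basis:** state power of about 49% with 18 evaluable per group (54% with 20) for 60 µg/L and SD 90 µg/L, or state a detectable difference of about 100 µg/L at 90% power with 18 per group.
2. **If about 90% is to stand:** name the baseline-adjusted repeated-measures analysis of the 6 to 72 hour values as the primary IL-6 analysis. State the assumed average difference over that window and the correlation structure, with their source, and compute the power from them. Show how it changes with decaying correlation and a smaller average effect, since the working above then gives 81–86% and 58–68%; this route may not restore 90%.

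Either is a rewording in two places with no extra patients. The cost is a less favourable power statement under the first, or a commitment to one primary model and disclosed assumptions under the second. If the sponsor wants 90% for the 24-hour comparison itself, that is a different design, with about 49 evaluable (55 randomised) per group.

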5.4 Criteria for In- and Exclusion

As our hypothesis proposes a relevant effect on any person undergoing treatment by va-ECMO post CPR, the criteria for in- and exclusion of study participants are in accordance with the clinical indication for this procedure as specified in the standard operating procedures of the University Cardiac Arrest Center Hamburg:

Indications:

- Age: 18 to 75 years
- cardiopulmonary arrest with
- \circ a potentially reversible cause
- o an initially observed rhythm qualifying for defibrillation and
- sufficient CPR prior to va-ECMO

relative contraindications:

- severely lowered pH and/or severely increased lactate in arterial blood gas analysis at the time of evaluation
- protracted CPR for >30 minutes prior to evaluation for va-ECMO

absolute contraindications:

- Do-not-resuscitate (DNR)-order stated by the patient prior to current event
- context of palliative care
- severe persisting neurological impairment, proven or highly likely at the time of evaluation for va-ECMO
- severe trauma
- relevant acute hemmorhagic event
- presence of comorbidities with severe reduction of life expectancy (like, but not limited to chronic pulmonary disease, chronic heart failure prior to event, hepatic cirrhosis, malignoma)

